10.2.2.3 Time to Progression (TTP) from Start of Sunitinib

TTP defined as time from Sunitinib Start Visit to date of first observed progression or date of death if the death was due to disease progression (whichever came first). Progressive disease is defined by RECIST v1.1 criteria and by clinical evaluation.

Note: For intermediate-risk patients included in the trial according to protocol versions before version Final 4.0, the first imaging assessment after nephrectomy will be used as baseline for evaluation of TTP, irrespective of whether or not the imaging assessment coincided with sunitinib treatment start. Further details will be provided in the SAP.

10.2.2.4 Number of Infiltrating CD8+ T-Cells

At Nephrectomy two (2) separate biopsies from viable tumor tissue (10x10x5 mm) will be collected at least one (1) cm from each other from the resected renal tumor will be sent to [REDACTED], where they will be assessed centrally. The samples will be labelled with the patient's unique screening number, date and Tumor No. The study specific Laboratory Manual, which will be provided to all sites participating in this study will include full details on collection, handling and transport. All samples will be destroyed after analyses have been performed. Immunohistochemically stained sections of formalin-fixed, paraffin-embedded tissues will be analyzed.

The numbers of infiltrating CD8+ T-cells are evaluated per sample as follows: In the light microscope the area of the highest concentration of CD8+ T-cells are located. At this place an image is taken with the 10x objective. The position of the tissue section is then moved to an area just adjacent and a new photo is taken. This procedure is then repeated once more resulting in three (3) photos with the 10x objective adjacent to each other. The number of CD8+ T-cells are then manually counted from photo out-prints. Each photo covers 580x435 micrometer from the tissue section. From these figures the number of CD8+ T-cells/mm² are calculated. Two (2) different Investigators without prior knowledge of the patients' treatment assignment or clinical information will do these assessments. In case of discrepancy, the slides will be re-examined in order to reach consensus.

The median number of CD8+ T-cells from the six (2x3) counted areas per patient will be evaluated per stratum and in total from the two (2) treatment arms.

Additionally a part of the formalin-fixed and paraffin-embedded tumor tissue prepared at [REDACTED], will be transported to the GLP compliant laboratory [REDACTED], where a validated automated quantification of intratumoral CD8+ T cells, using whole slide scanning instruments, will be performed. The immunohistochemistry

kit that will be used for revelation of CD8 staining at the Histalim Laboratory is a CE marked In Vitro Diagnostic Medical Device (IVD). The digitalization (Nanozoomer) of stained tissue slides follows 21 Code of Federal Regulations (CFR) part 11 guidelines. The tumoral area will be delineated by a trained operator and the surface of CD8 labeling percentage will be assessed in the delineated area. Finally, the analysis tool for semi-automated image quantification follows 21 CFR Part 11. All samples will be destroyed after analyses have been performed.

NB. For applicable patients one (1) pre-biopsy is taken for diagnostic purpose. If this is performed after consenting and before vaccination (for vaccine arm) this biopsy will be regarded as a baseline sample and will be analyzed as described above.

[REDACTED]

[REDACTED]

[REDACTED]

[REDACTED]

[REDACTED]

[REDACTED]

[REDACTED]

[REDACTED]

[REDACTED]

[REDACTED]

[REDACTED]

[REDACTED]

[REDACTED]

[REDACTED]

10.3 Drug Concentration Assessments - N/A

10.4 Demographic and Other Baseline Characteristics

10.4.1 Demographic and Baseline Data

The following demographic and baseline data will be collected at the Screening Visit:

- Date of birth
- Sex
- Race (White, Asian, Black, American Indian or Alaska Native, Native Hawaiian or Other Pacific Islander)

Full information about the patients' Social Security Number and name is to remain confidential in the records of the respective Investigator.

10.4.2 Medical and Surgical History

MEDICAL AND SURGICAL HISTORY (EXCLUDING MRCC)

Clinical relevant past and present medical and surgical diagnoses non-related to RCC will be recorded at Screening in the eCRF. Medical History will be coded using the Medical Dictionary for Regulatory Activities (MedDRA) version 17.1.

MEDICAL HISTORY (MRCC)

The following medical history related to mRCC will be collected at Screening:

- Date of RCC diagnosis
- Primary tumor stage as defined by the American Joint Committee on Cancer's (AJCC's) TNM classification system [30]
- RCC symptoms including severity grading (NCI CTCAE version 4.0) [2]

The diagnosis of RCC will be confirmed by histopathological local assessment of tumor tissue after nephrectomy.

10.4.3 Efficacy Assessments by Imaging

The locally assessed CT scan in conjunction with screening is to verify patient eligibility. This scan will be performed within 3 weeks before the Screening Visit unless a CT scan has been done in clinical routine within 6 weeks prior to the Screening Visit.

Brain imaging: every subject must have had a MRI of the brain during the screening period unless a brain imaging by (preferably by contrast enhanced) MRI or CT was performed within the 6 weeks before randomization date. The MRI brain may be replaced by a CT brain if the subject does not tolerate the MRI procedure.

On study, MRI (preferably contrast-enhanced) of the brain (or contrast-enhanced CT if not possible otherwise) should only be performed on the indication of evocative neurological symptoms.

Tumor response will be evaluated by means of CT preferably, contrast enhanced of the chest, the upper and lower abdomen (including pelvis) and all other suspected sites of disease. The tumor response will be evaluated according to RECIST v1.1. [1] at baseline and for all repeated measurements according to the Schedule of Study Events, *Section 7.2.1*.

CT scan assessments will be done both by a local radiologist trained in the study protocol and by a central assessor at the designated imaging CRO, [REDACTED], without knowledge of the patients' treatment assignment and Heng-risk profile. Central assessments will form the basis for endpoint evaluations (PFS, ORR, TTP, TTF and tumor response rate). Central assessments will be done in accordance with a separate study-specific imaging protocol provided by [REDACTED].

A study specific instruction describing the handling, transferring, blinding, distribution, assessment, result processing, and filing of data will be handed out to all involved personnel.

CT scans performed at Sun-Start Visit five (5) to eight (8) weeks after nephrectomy will be used for evaluation of PFS from start of sunitinib, *Section 10.2.2.1*. Note: For intermediate-risk patients included in the trial according to protocol versions before version Final 4.0, the first imaging assessment (i.e. CT scan) after nephrectomy will be used.

CT scans performed at Sun-Start Visit five (5) to eight (8) weeks after nephrectomy will be used for evaluation of response rate from start of sunitinib, *Section 10.2.2.2*. Note: For intermediate-risk patients included in the trial according to protocol versions before version Final 4.0, the first imaging assessment (i.e. CT scan) after nephrectomy will be used.

Centrally assessed CT scans performed in conjunction with screening and at the first post-nephrectomy assessment will be used to assess tumor response rate between screening and the first imaging assessment (i.e. CT scan) post-nephrectomy.

The following information will be collected and used for the assessments if response is CR, PR, PD, SD, or "Not evaluable":

- Date of Abdomen CT scan
- Date of Thorax CT scan
- Site of metastases (including specification of target and non-target lesions at Sun-Start Visit five (5) to eight (8) weeks after nephrectomy see *Section 10.2.2.2* and [1])
- Sum of the diameters for all target lesions, see *Section 10.2.2.2* and [1]
- New lesions, see *Section 10.2.2.2* and [1]

If CT cannot be used for some reason, MRI is acceptable. The same modality has to be used at all visits.

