7 INVESTIGATIONAL PLAN

7.1 Study Design and Plan-Description

The study is an open-label, randomized, controlled, two (2) armed, multicenter, phase II study. Intermediate- and high-risk mRCC patients according to Heng criteria are eligible for participation [4]. Stratified randomization based on Heng-risk categories applies. The patients are randomized in a consecutive order to one (1) of the following two (2) treatment arms when eligibility has been confirmed;

- (i) Two (2) doses of Intuvax (10×10^6 DCs) administered intratumorally into the primary tumor 14 ± 3 days apart followed by nephrectomy at least three (3) days after the second vaccine dose.

AND

Sunitinib treatment initiated five (5) to eight (8) weeks after nephrectomy, administered dose in accordance with the SmPC/USPI.

- (ii) Sunitinib treatment initiated five (5) to eight (8) weeks after nephrectomy, administered dose in accordance with the SmPC/USPI.

The estimated number of patients to be randomized in the study is around 90. The patients will be randomized in a 2:1 (vaccine treatment arm [i]:control treatment arm [ii]) ratio. Stratification will be done at randomization for intermediate- and high-risk patients.

Patients randomized to treatment arm (i) are scheduled for 12 study visits and patients randomized to treatment arm (ii) are scheduled for 10 study visits during a study period of 78 weeks, see list below and *Figure 1*. In addition, all patients being exposed to any of the Investigational Medicinal Products (IMPs) will have a safety evaluation done for collection of SAEs up to 30 days after last dose of IMP administered in the study. The following visits apply for the two (2) patient populations:

- Screening Visit (Screening)
- Vaccination 1 Visit (Vacc1), applicable for patients randomized to treatment arm (i)
- Vaccination 2 Visit (Vacc2), applicable for patients randomized to treatment arm (i)
- Nephrectomy Visit (Nephrectomy)
- Sunitinib Start Visit (Sun-Start), five (5) to eight (8) weeks after Nephrectomy
- Sunitinib Follow-up Visits (SFU[6W] and SFU[12W]), every 6 weeks for 12 weeks or until locally CT-verified PD whichever occurs first
- Sunitinib Follow-up Visits (SFU[24W], SFU[36W], SFU[48W], and SFU[60W]), every 12 weeks until End-of study or until locally CT-verified PD whichever occurs first
- End-of-Study Visit (End-of-Study)

[figure not shown]

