7.2.1.6 SFU[6W], SFU[12W], SFU[24W], SFU[36W], SFU[48W], and SFU[60W]

These visits are applicable for all patients unless locally CT-verified PD occurs. In case of PD this visit should be considered the End-of-Study Visit.

If SFU[60W] is scheduled ≥ 76 weeks since Screening this visit should be considered the End-of-Study Visit, *Section 7.2.1.7*.

TIME WINDOWS:

SFU[6W]: 6 weeks (± 7 days) after Sun-Start Visit
SFU[12W]: 12 weeks (± 7 days) after Sun-Start Visit
SFU[24W]: 24 weeks (± 7 days) after Sun-Start Visit
SFU[36W]: 36 weeks (± 7 days) after Sun-Start Visit
SFU[48W]: 48 weeks (± 7 days) after Sun-Start Visit
SFU[60W]: 60 weeks (± 7 days) after Sun-Start Visit

NB: The CT/MRI scans do not have to be done the very same day as the corresponding study visits. However, each CT/MRI scan has to be done within the specified time window for the corresponding visit.

ACTIVITIES AND ASSESSMENTS:

The same activities and assessments will be done at these visits as was done on Sun-Start Visit except for auto- and alloimmunization, *Section 7.2.1.5*. In addition to dispense of sunitinib, the site personnel will collect unused and empty sunitinib packages (distributed at the previous visit) from the patient for drug accountability, *Section 9.1.4*.

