6.3.6 Secondary Efficacy Analyses

PFS from start of sunitinib according to RECIST 1.1

PFS from start of sunitinib treatment will be derived as date whichever occurred first of any cause of death or date for first tumor progression (which is date for centrally assessed CT performed, according to RECIST 1.1) minus date for start of sunitinib treatment plus 1 day.

For the analysis of PFS only deaths occurring before end-of-trial will be accounted for in the analysis.

Analysis of PFS will be evaluated the following way:

Survival functions will be displayed graphically using Kaplan-Meier plots, and life table statistics will be produced including summaries of number of events and censored observations. Estimates of cumulative 25%, 50% (median) and 75% percentiles of survival with corresponding 95% confidence intervals will be calculated.

Comparison between Intuvax+sunitinib, vs. sunitinib alone will be done using a stratified log-rank test (controlling for strata intermediate/high risk), separate analyses will also be done by strata.

With protocol versions before version 4.0, intermediate risk patients did not have to initiate treatment with sunitinib at a fixed time point according to the visit schedule. Consequently some patients were never started on sunitinib, and in some cases sunitinib treatment was initiated at a later time point. The sunitinib start date constitutes the baseline time point for PFS according to protocol version 4.0 and after. In the analyses, patients who either had a delay or never started sunitinib will be included under the assumption that sunitinib treatment would have been initiated according to the final design, the date of the visit following the nephrectomy visit will be used as baseline.

Another issue that will be considered in the analysis is that some patients may have been discontinued based on general clinical disease progression as evaluated by investigator from symptoms/signs of disease, rather than based on a PD according to RECIST 1.1. For the analysis such cases will be handled strictly based on the RECIST 1.1 evaluation, thus if a patient is withdrawn without a CT confirmed PD the subject will be censored at last CT

Analyses will be based on FAS and repeated for separately by strata..

Proportion of Objective Response Rate (ORR) and Disease Control Rate (DCR) from start of sunitinib

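### Scanning stops at local PD but PFS uses the central read, so local PD not confirmed centrally is probably censored informatively, and no visible sensitivity analysis tests this

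*Protocol*

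**What the plan says.** **When scanning stops.** Protocol 7.2.1.6 says of the sunitinib follow-up visits, which carry the scans: "These visits are applicable for all patients unless locally CT-verified PD occurs. In case of PD this visit should be considered the End-of-Study Visit". Protocol 7.1 has the same rule ("every 6 weeks for 12 weeks or until locally CT-verified PD whichever occurs first", with matching wording for the 12-weekly visits), and SAP 4.1 repeats it. Under Protocol 8.5, PD on sunitinib is a listed reason for withdrawal, and patients who stop treatment for safety reasons return for visits only until PD.

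**Whose read counts.** Protocol 10.4.3 has each CT read by a local radiologist and by a central assessor, then states: "Central assessments will form the basis for endpoint evaluations". PFS is among the endpoints it names. SAP 6.3.6 dates progression in PFS accordingly: "which is date for centrally assessed CT performed, according to RECIST 1.1".

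**Censoring.** SAP 6.3.6 deals with patients discontinued for clinical progression without RECIST PD and rules that "if a patient is withdrawn without a CT confirmed PD the subject will be censored at last CT". It also counts in PFS only deaths before end-of-trial, without saying whether that is the patient's end or the whole trial's.

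**What is tested.** PFS gets a stratified log-rank comparison of the arms and separate analyses by risk stratum (SAP 6.3.6). It is the first-listed secondary efficacy endpoint (SAP 3.2).

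**The concern.** One reader decides when imaging ends and another decides whether an event occurred. When the local reader calls PD and the central reader does not, the patient leaves scheduled imaging without an event, and no later scan exists on which central PD could be seen. The visible text asks for neither central confirmation before scanning stops nor continued imaging until central PD.

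Kaplan-Meier and the log-rank test assume that patients censored at a given time have the same later risk as those who stay under observation. Patients censored because a radiologist has just judged their disease to be worse probably do not. The likely result is a PFS curve that is too high. If disagreement is more frequent in one arm, the comparison between arms is distorted as well. A single central-read result cannot show whether either has happened.

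**Working it through.** **1. No planned figure to reproduce.** Protocol 12.2 and SAP 4.2 give about 90 patients randomized 2:1 (60 and 30) with no power calculation. The documents give no PFS effect, expected number of PFS events or local/central disagreement rate. Every rate below is an assumption.

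**2. The path of a discordant patient.**
- Local PD at a scan: that visit becomes End-of-Study (Protocol 7.2.1.6).
- The central read of the same scan is not PD: no progression date for PFS (SAP 6.3.6).
- No later scheduled scan, so the patient is censored at the last CT (inferred from SAP 6.3.6, which does not name this case).

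**3. Upper bound on the median.** If a share *f* of all PFS events becomes censored observations at about the same times, the estimated exponential hazard falls from *h* to (1 - *f*)*h*. The median, ln 2 / hazard, is multiplied by 1/(1 - *f*):
- *f* = 0.10: 1/0.90 = 1.11 (+11%)
- *f* = 0.20: 1/0.80 = 1.25 (+25%)
- *f* = 0.30: 1/0.70 = 1.43 (+43%)

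**4. Smaller base.** Deaths without PD, and central PD called before local PD, remain events. If local PD calls lead to 70% of events (assumption) and 10-30% of those calls are unconfirmed, the shares lost are 0.7 × 0.10 = 0.07 and 0.7 × 0.30 = 0.21:
- 1/0.93 = 1.08 (+8%)
- 1/0.79 = 1.27 (+27%)

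**5. Simulation on the planned scan schedule.** Assumptions: exponential central PFS with a 35-week median; scans at 6, 12, 24, 36, 48 and 60 weeks, plus one at about 66 weeks, after Sun-Start. In a share *d* of patients who would have central PD, local PD is called one scan earlier and the patient is censored there.

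| *d* | 48-week PFS, Kaplan-Meier | PFS events per 90 patients |
|---|---|---|
| 0 | about 39% | about 66 |
| 10% | 42% | 59 |
| 20% | 46% | 53 |
| 30% | 50% | 46 |

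The formula in step 3 gives nearly the same: 0.5^(48/35) = 0.387, and raising this to the powers 0.9, 0.8 and 0.7 gives 42.5%, 46.7% and 51.4%. With a 24-week median, 48-week PFS of 25% became 28% to 41% over *d* = 10% to 40%. With a 48-week median, 50% became 53% to 65%.

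**6. Hazard ratio with no true treatment effect** (35-week median, vaccine versus control):

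| *d*, vaccine / control | HR, censored as in the SAP | HR, local PD counted as an event |
|---|---|---|
| 20% / 20% | 0.99 | 0.99 |
| 10% / 20% | 1.08 | 0.96 |
| 10% / 30% | 1.27 | 0.96 |
| 20% / 10% | 0.90 | 1.02 |
| 30% / 10% | 0.77 | 1.02 |

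The same runs with no disagreement gave HRs of 0.98 to 1.00, so simulation noise is about 0.02. Equal disagreement leaves the HR near 1. Unequal disagreement moves it either way, and counting local PD as an event removes most of the shift.

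**7. Search for an existing check.** The per-protocol repeat (Protocol 12.1.6) changes the patients, not the reader or the censoring. TTP (SAP 6.3.6) adds clinical progression but drops deaths and does not name local RECIST PD as an event. SAP 6.6 uses observed cases. The visible titles in SAP Appendix 1 include no local-read PFS and no table of reader agreement.

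**The case against.** **The SAP does not state this rule.** The censoring sentence sits in a paragraph about clinical progression and names no reader. That stands: censoring of discordant patients is an inference, though a fair one, because the same section defines the progression date by the central CT.

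**Deaths may recover some events.** Protocol 7.5 defines the end of study for the whole trial, and survival is collected after withdrawal (Protocol 8.5 and 11.3). If end-of-trial in SAP 6.3.6 has that meaning, a discordant patient who dies before it may count as an event, against the censor-at-last-CT sentence. The ambiguity is real and could reduce the bias.

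**Not every unconfirmed call is early progression.** Some may be ordinary reader variation with no raised hazard, and censoring those patients adds no bias. This stands, and it is one reason why 11-43% is a ceiling. The simulation is also near an upper bound, because each discordant patient has central PD at the next scan.

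**The local radiologist may be masked.** A reader might infer that local readers know the arm and central readers do not. Protocol 10.4.3 does not establish this: its phrase on lack of knowledge of treatment and Heng risk can be read as covering both readers. Protocol 9.5 says only that the study is open label. On the other side, Protocol 10.2.2.2 lets the treating physician's opinion prevail on non-target progression, so knowledge of the arm could still enter the local call. Bias between arms is therefore possible, not shown.

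**An analysis may exist out of sight.** SAP 6.1 has redacted items, Appendix 1 has redacted titles and gaps in its table numbers, and the imaging protocol cited in Protocol 10.4.3 is not among the documents. The absence of a sensitivity analysis can be claimed only for the visible text.

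**The stakes are limited.** The trial is exploratory and unpowered, and PFS is secondary. This limits the consequence but does not remove it, because PFS is still tested between arms.

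**Conclusion.** The concern holds in limited form. Local PD ends imaging, PFS follows the central read, and by inference a local PD that is not confirmed centrally is censored at a time probably linked to prognosis. Median PFS could be overstated by at most about 11-43% if 10-30% of all PFS events were lost, or about 8-27% if local PD calls lead to 70% of events. Both ranges rest on exponential times and assumed disagreement rates, and neither is an expected value.

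A reader might go further and conclude that the treatment comparison is biased. The documents do not support that: the HR stays near 1 if disagreement is equal across arms, and nothing in them shows that it is unequal or in which direction. TTP shares the problem, as in part do duration of response and TTF. OS and 18-month survival, the primary endpoints, do not depend on either CT read.

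**What to change.** Keep central-read PFS as the main analysis. In SAP 6.3.6:

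1. Add one PFS sensitivity analysis with the event as the earliest of central PD, local CT-verified PD or death, using the same stratified log-rank test.
2. Add a table of local/central disagreement on PD by arm.
3. State whether end-of-trial, for deaths counted in PFS, means the patient's end or the whole trial's, and say explicitly how a local PD without central PD is handled.

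Leave clinical progression out of the sensitivity analysis. The SAP deliberately excludes it from PFS, and merging it in would stop the analysis from isolating the reader question.

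This is a cheap improvement: one analysis, one table and a clarification. The local reads are already made under Protocol 10.4.3, so no new scans are needed. The downside is a second PFS figure that may be partly unblinded; it should be labelled as a robustness check.

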10.4.4 Prior and Concomitant Medication/Therapy

Prior medication/therapy is defined as medication/therapy administered prior to Screening Visit. All medication/therapy administered after Screening Visit are considered concomitant medication/therapy. Prior medication/therapy will be indicated as past or ongoing at Screening.

Prior medications taken within one (1) month prior to Screening and current ongoing treatment will be recorded at the Screening Visit on the concomitant medication page of the eCRF. Changes in concomitant medications will be recorded at all following visits throughout the study. For information on Concomitant Medication restrictions, see *Section 9.6*.

The following information will be collected and recorded in the eCRF: Drug name (product name), route, dose and units, frequency, indication, reference to AE if applicable, start date, end date or ongoing at the end of the study will be recorded.

Coding of prior and concomitant medications will be done using World Health Organization (WHO) Drug Dictionary.

